
40% less patient-controlled opioid analgesia use than controls during the 48-hour post-operative period, with lower pain ratings^{26, 27, 30}. This series of studies was the first to demonstrate the potential of brain stimulation technology to be part of a standard post-operative pain-management strategy, however TMS is more complicated to deliver than tDCS, has more adverse events, and is more cumbersome in the post-operative setting. In two independent preliminary pilot studies, the PI has shown that tDCS can reduce post-operative PCA use by as much as 46% while simultaneously reducing subjective pain ratings. Thus, a handful of preliminary studies have demonstrated the potential for brain stimulation techniques to adjunctively manage post-operative pain, but a more definitive trial is needed to evaluate the efficacy of tDCS using a more rigorous experimental design. Further more data is needed to determine optimal tDCS dosing parameters before tDCS will become a viable clinical intervention for post-operative pain across surgical specialties.

Aim-1: Determine the effects of transcranial direct current stimulation (tDCS) on post-operative pain, patient-controlled analgesia (PCA) use, and post-surgical complications during the 48-hour post-operative period following total knee arthroplasty (TKA) or total hip arthroplasty (THA).

Hypothesis 1: Real tDCS (over sensory/motor and dorsolateral prefrontal cortices) will be associated with decreased PCA morphine-equivalent usage (primary outcome), decreased pain ratings (secondary outcome), and decreased post-operative complications compared to sham tDCS.

Aim-2: Collect preliminary data regarding dose-dependent effects of tDCS on post-operative pain, PCA morphine-equivalent usage, and 6-month outcomes.

Hypothesis 2a: The analgesic benefits of tDCS will be dose dependent such that one 20-minute post-operative tDCS session will be superior to sham, two sessions will be superior to one session, and four sessions will produce the largest analgesic effects in the present study.

Hypothesis 2b: Patients receiving higher doses of real tDCS will evidence lower incidence (and dose) of 6-month opioid medication use, reduced pain, and better quality of life.

B. BACKGROUND AND SIGNIFICANCE

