tDCS Effects on Post-Procedural Pain Pilot:¹⁰² Recently, the PI conducted the first-ever pilot study on the effects of tDCS on post- Endoscopic Retrograde Cholangiopancreatography (ERCP) pain. Nineteen Caucasian females (mean age=37.2 StdErr=2.4) were enrolled. After ERCP, participants were randomly assigned to receive 20-minutes of tDCS with anode over the left-prefrontal cortex and cathode over the gut representation of the sensory cortex. No serious adverse events were associated with tDCS. Side-effects of tDCS were limited to tingling (42%), itching (47%) and mild stinging (11%) under the electrodes. Patients that received a single 20-minute dose of real tDCS used 22% less total hydromorphone than those that received sham at the end of the 24-hour inpatient post-procedural period (Cohen's $d=.38$). The slope of the cumulative PCA usage curve was significantly steeper in the sham tDCS group compared to real ($t(355)=10.80, p<.0001$). VAS pain scores suggested an arithmetic advantage for real tDCS compared to sham (not statistically significant likely due to limited power). *Results from this pilot feasibility study suggest that tDCS is safe, well-tolerated, and may be able to reduce post-ERCP opioid requirements without increasing subjective pain ratings.*

[figure not shown]
tDCS Effects on Post-Total-Knee-Arthroplasty (TKA) Pain Pilot: In a very recent preliminary pilot study, the PI randomly assigned 40 patients undergoing unilateral TKA to receive a total of 80 minutes of real ($n=20$) or sham tDCS ($n=20$) with the anode over the knee representation of the motor strip and cathode over the right dorsolateral prefrontal cortex. 20-minute tDCS treatments were delivered: 1) in the PACU, 2) 4 hours later, 3) the morning of post-operative day-1, and 4) the afternoon of post-operative day-1. VAS pain and mood ratings were collected every 4 hours following surgery provided that patients were awake. The slopes of the cumulative PCA usage curves were significantly different between groups, and those TKA in the real tDCS group used 44% less PCA dilaudid at 48-hours post-op ($p=.007$; Cohen's $d=1.0$). Despite significantly lower PCA dilaudid levels, VAS ratings of pain-on-average were also significantly lower in the real tDCS group ($t(37)=2.28, p=.029$). No adverse events or serious adverse events were encountered. There were no cases in which tDCS needed to be discontinued due to patient discomfort or tDCS-related complications.

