This dosing scheme will permit investigators to determine whether more stimulation over time is superior to less stimulation, as well as to determine the efficacy of motor tDCS in the management of perioperative pain.

Blind Maintenance: To ensure blinding, specially-developed software will be utilized to switch the tDCS on and off without any intervention from the patient or experimenters. This will be controlled via a silent solid-state relay driven by an Ontrak ADU218 (Ontario, Canada). For Sham tDCS sessions the stimulator will be turned off following 45s. The initial sham stimulation mimics the transient scalp sensation that is perceived when the stimulator is initially switched on. The order of treatment administration will be encoded in the software so that the administrator only enters a patient number and a session-number to start stimulation without knowing whether those specific numbers are associated with active or sham tDCS. The double-blind may only be broken if the clinical presentation of the patient suggests potential cognitive dysfunction, seizure activity, severe headache or extreme skin irritation under the electrodes.

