Statistical Analysis and Power: The orthopaedic surgeons at the Ralph H. Johnson VAMC conduct ~100 unilateral total knee arthroplasties and ~50 unilateral total hip arthroplasties each year . Thus, in order to meet the proposed n-size of the current study, 24 (out of 100) participants will need to be eligible and interested in participating in the trial each year. We will over recruit to permit for drop-outs and participants lost to follow-up. For analysis of primary outcomes associated with Aim-1, participants receiving any active tDCS (groups 1,2 & 3) will be collapsed and compared to the sham-only group. Multivariate multiple regression will be used with group-assignment entered into the model as a binary predictor. Surgery and anesthesia duration, depression & anxiety scores, sex, age, pre-tDCS pain, (ROM) Means and pre-op chronic opioid status will be entered into the model as covariates to permit for statistical control of these potentially confounding variables. Overall differences between real and

sham tDCS groups will then be examined for our primary outcomes: total post-op PCA morphine-equivalent dose, VAS pain-on-average ratings, and mean number of post-operative complications. Using the most conservative effect-size estimate from our series of pilot studies ($d=.70$), with 90 patients in the active tDCS group and 30 in the active-sham group, power is good to detect significant effects if they exist ($\alpha=.016$ (corrected for multiple DV's); $1-\beta >.80$; see figure 9). For Aim-2, MANCOVA will be conducted using all 4 groups and all primary dependent measures in the same model (controlling for surgery and anesthesia duration, depression & anxiety scores, pre-tDCS pain, physical rehab measures and chronic opioid status). With four groups of 30 patients each, assuming a moderate effect size $f^2(V)=.2$, and alpha of .05, power is good detect significant main effects in the model ($1-\beta >.80$). Secondary analyses will be conducted to evaluate long-term effects of tDCS on pain, functioning and quality of life (i.e., 2-wk, 4-wk, 8-wk, 3-month and 6 month-follow-up).

Problems/Challenges/Potential Pitfalls: The proposed tDCS device is an FDA-approved iontophoresis device, and its use for tDCS applications is off-label. The tDCS procedure is minimal-risk and FDA-

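### The plan gives two different primary-outcome lists for Aim 1, and names no test that uses the dose order predicted in Hypothesis 2a

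*Combined protocol and SAP*

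**What the plan says.** **Outcome hierarchy.** Hypothesis 1, under Aim-1, predicts "decreased PCA morphine-equivalent usage (primary outcome), decreased pain ratings (secondary outcome), and decreased post-operative complications compared to sham tDCS". PCA use is primary, pain is secondary, and complications carry no label. Section D, Statistical Analysis and Power, refers to "our primary outcomes: total post-op PCA morphine-equivalent dose, VAS pain-on-average ratings, and mean number of post-operative complications", so all three are primary there. Of the method it says: "Multivariate multiple regression will be used with group-assignment entered into the model as a binary predictor". Differences between active and sham are then examined on those outcomes, with the three active groups pooled (90 versus 30), d=.70, alpha .016 to correct for several outcomes, and power above .80. It does not say whether one significant outcome is enough, or whether the multivariate result must be significant first.

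**Dose order.** Hypothesis 2a predicts that one session beats sham, and then that "two sessions will be superior to one session, and four sessions will produce the largest analgesic effects in the present study". The tDCS Dosing section says: "This dosing scheme will permit investigators to determine whether more stimulation over time is superior to less stimulation". The only Aim-2 analysis is this: "MANCOVA will be conducted using all 4 groups and all primary dependent measures in the same model". Its power statement concerns main effects. No trend test, planned contrast or pairwise comparison is named anywhere. Aim-2 itself is worded modestly: "Collect preliminary data regarding dose-dependent effects of tDCS on post-operative pain, PCA morphine-equivalent usage, and 6-month outcomes".

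**The concern.** Both outcome lists are current text, and pain cannot be secondary in one and primary in the other. A trial with a clear pain result and a null PCA result is a primary success under the analysis section and a secondary finding under Hypothesis 1. If this stays open, the label can be chosen after the data are seen. The section on Impact on Clinical Practice and Future Studies says the findings will inform whether a multi-site trial is needed, so the label has a consequence.

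For Aim 2, the question is whether more stimulation is better than less. A significant MANCOVA says that some group differs from another on some combination of outcomes. It gives no sign and no order. Any comparison used to supply the order would be chosen afterwards.

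**Working it through.** **1. The plan's own Aim-1 figure.** Inputs from Statistical Analysis and Power: 90 versus 30, d=.70, alpha .016. Two-sided testing is assumed, as the plan does not state it. Noncentrality = d/√(1/90+1/30) = .70/.2108 = 3.320 on 118 df. The critical t is 2.444, and power is **.808**, so the stated figure reproduces. At alpha .05 the critical t is 1.980 and power is .909.

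**2. Error control.** 3 × .016 = .048. If the outcomes are independent, 1 − (1−.016)³ = .047. Simulation under no effect gives .047, .044 and .043 at outcome correlations 0, .3 and .5. There is no inflation.

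**3. How often the two lists disagree.** Simulation with 90 versus 30, three normal outcomes, unadjusted t-tests and at least 20,000 trials per row. Repeat runs differ by about .005 or less. Aim 1 is counted positive if any outcome has p<.016. The last two columns are shares of all trials.

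| True effect | Correlation | Positive | Positive, PCA p≥.016 | Positive, PCA p≥.05 |
|---|---|---|---|---|
| d=.70 on all three | 0 | .99 | .185 | .089 |
| | .3 | .97 | .167 | .075 |
| | .5 | .95 | .147 | .061 |
| d=.70 on pain only | 0 | .81 | .80 | .77 |
| | .3 | .82 | .80 | .775 |
| | .5 | .82 | .80 | .78 |

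The last column is the fairer measure of conflict. If PCA were the sole primary outcome it would be tested at .05, so a trial with PCA p between .016 and .05 would be a primary success on either list. The pain-only rows are a bound.

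The role of the multivariate test also matters. With pain only at d=.70, requiring an overall Hotelling test at an assumed .05 first changes the success rate from .81–.82 to .76–.81.

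**4. Omnibus test versus contrasts on PCA.** 30 per arm, 116 df, two-sided .05. Effects are in SD of benefit for 0, 1, 2 and 4 active sessions. All patterns are assumptions:
- Pattern A, 0/.175/.35/.70, is linear in sessions up to .70.
- Pattern B, 0/.38/.69/1.0, uses the one-session ERCP and four-session TKA pilot effects from section C, with their midpoint between. The two pilots differ in procedure and electrode placement.

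Formulas:
- Omnibus F (3 df): λ = 30·Σ(m−m̄)².
- Contrast: noncentrality = Σcm/√(Σc²/30).
- For sessions 0,1,2,4: c = (−1.75, −.75, .25, 2.25), Σc² = 8.75.
- For 1,2,4 among active arms: c = (0, −1.333, −.333, 1.667), Σc² = 4.667.

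Pattern A worked through:
- Omnibus: λ = 8.04, power .64.
- 0,1,2,4 contrast: 1.531/.540 = 2.835, power .80.
- Active-arm contrast: .8167/.3944 = 2.071, power .54.

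| Pattern | Omnibus | 0,1,2,4 contrast | 1,2,4 contrast, active arms |
|---|---|---|---|
| A | .64 | .80 | .54 |
| A, active arms reversed | .64 | .05 | .48, in the opposite direction |
| B | .93 | .98 | .65 |
| B, active arms reversed | .93 | .08 | .65, in the opposite direction |
| All active arms at .70 | .79 | .61 | .05 |
| All active arms at 1.0 | .98 | .89 | .05 |

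Reversing the active arms leaves the omnibus power unchanged. This holds for any pattern, because relabelling arms does not alter the test. The 0,1,2,4 contrast responds to order but includes sham, so it often rejects when every dose works equally. Only the active-arm contrast keeps its 5% level in that case.

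**5. Precision of single steps.** The 95% CI half-width for adjacent arms is t(116)·√(2/30) = 1.981 × .2582 = .51 SD. Power for a .175 SD step is about .10.

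**The case against.** The strongest defence is that the plan already adjusts alpha for three outcomes, that those outcomes match the three effects named in Aim-1, and that this is called a pilot. Much of that stands. A reader might infer inflated error or overstated power; steps 1 and 2 show neither at the plan's own d=.70. A reader might also think any PCA result is in dispute. It is not: a PCA result with p<.016 is a primary success on both lists.

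The pain-only scenario is also not what the pilots suggest. In the TKA pilot, PCA use fell (d=1.0) and pain fell too: t(37)=2.28, about 2.28·√(1/20+1/19) = .73 if the 39 patients split 20/19. In the ERCP pilot, PCA use fell and pain was not significant. The all-respond rows are therefore the better guide to size.

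On Aim 2, it would be too strong to say that dose is ignored or that the design cannot address it. The MANCOVA uses all four groups, and its adjusted means can describe an order, which may suit an aim labelled preliminary. But description is not the determination that the tDCS Dosing section promises, and the preliminary label does not supply a test. It lowers the severity.

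A reader may also ask whether d=.70 is justified, given the ERCP pilot's d=.38. That is a separate matter and does not bear on outcome labels or ordering.

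**Conclusion.** Both parts hold, and both should be fixed.

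(a) The documents contradict each other on the primary outcome and leave the Aim-1 success rule undefined. If all three outcomes respond at d=.70, 6–9% of trials would be positive only through pain or complications with PCA p≥.05, or 15–19% with PCA p≥.016. The upper bound, with pain alone responding at d=.70, is .77–.78 (about .80 with PCA p≥.016). These figures assume normal outcomes, two-sided unadjusted tests, correlations of 0 to .5 and no dropout. The documents do not show which hierarchy was intended.

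(b) Hypothesis 2a has no test that uses its order, and the MANCOVA p-value cannot show order or direction. That conclusion needs no assumed dose-response pattern; only the power figures do.

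**What to change.** **(a) Before unblinding, reconcile Hypothesis 1 with Statistical Analysis and Power.** Either option resolves it.

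- *Option 1.* PCA morphine-equivalents (pooled active versus sham, covariate-adjusted) become the single primary outcome at two-sided .05, with power about .91 at d=.70. Pain and then complications are tested in fixed order as secondary outcomes. Cost: pain and complications lose primary status and are tested only if PCA is significant, and the PCA threshold loosens from .016 to .05.
- *Option 2.* Keep three primaries at .016, with power .81 at d=.70, and amend Hypothesis 1 to match. State that claims are made outcome by outcome, and say whether the multivariate test must be significant first. Cost: the stricter threshold on PCA stays.

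**(b) For Aim 2, pre-specify on PCA:**

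- a 1-df contrast in number of active sessions (0,1,2,4), for trend including sham;
- beside it, a 1,2,4 contrast among the active arms. Dose-response beyond active-versus-sham is claimed only from this one, and only in the predicted direction;
- estimates with CIs for 1 vs 0, 2 vs 1 and 4 vs 2, with the MANCOVA kept as supportive.

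Cost: wording and two contrasts, with no new data. The active-arm contrast has modest power (.54 and .65 under the two assumed patterns) and the step estimates are imprecise (about ±.51 SD). Both are acceptable for an aim labelled preliminary. The 0,1,2,4 contrast is also less sensitive than the omnibus test if all active arms share one effect (.61 versus .79 at d=.70).

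### The Aim-1 power claim of >.80 covers post-operative complications, but the documents report no complication effect, rate or SD to support it

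*Combined protocol and SAP*

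**What the plan says.** Section D, Statistical Analysis and Power, pools the three active groups against sham and lists the Aim-1 primary outcomes as "total post-op PCA morphine-equivalent dose, VAS pain-on-average ratings, and mean number of post-operative complications". The next sentence gives a single justification: "Using the most conservative effect-size estimate from our series of pilot studies ($d=.70"). The group sizes entered are 90 pooled active and 30 sham. It concludes that "power is good to detect significant effects if they exist", at alpha .016 (described as corrected for several dependent variables) with power above .80. No outcome is exempted.

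Section C, Preliminary Studies, reports these results for post-procedural and post-operative use:
- ERCP pilot: d=.38 for hydromorphone use; pain scores not significant.
- TKA pilot: d=1.0 for PCA use at 48 hours; average pain t(37)=2.28. On safety it says "No adverse events or serious adverse events were encountered".

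Section D, Dependent Measures, defines complications very broadly, from headache and nausea to infection and cardiovascular events. It gives no expected number per patient, SD or distribution.

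**The concern.** A power statement rests on an effect size that is plausible for the outcome in question. For complications there is none: no pilot result in the documents gives a group difference, a rate or a spread. The d=.70 has been carried over from other outcomes.

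This matters because complications are a count. The same standardised difference is a modest proportional reduction when events are frequent and a very large one when they are rare. A reader who takes the >.80 at face value cannot tell which case applies, yet Aim 1 and Hypothesis 1 both promise an answer on complications.

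**Working it through.** **1. Does the power statement cover complications?** Three outcomes are listed and .05/3 = .0167, which fits the stated .016. Complications are therefore one of the three.

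**2. Reproduce the stated power.** Inputs from Section D: n = 90 and 30, d = .70, alpha .016. Sidedness is not stated; two-sided is assumed.
- SE of d = sqrt(1/30 + 1/90) = .2108, and .70/.2108 = 3.320.
- Critical value z = 2.409, so power = Φ(3.320 − 2.409) = .819.
- The noncentral t with 118 df gives .808.

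The claim is met, narrowly: the smallest d with 80% power is .694.

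**3. Where could d=.70 come from?** The opioid figures are .38 and 1.0. For pain in the TKA pilot, 37 df implies 39 patients. Assuming a 20/19 split, d = 2.28 × sqrt(1/20 + 1/19) = .73. So .70 is close to the pain result, but it is not itself reported for any outcome. At the reported d=.38, power in this design is .26 (noncentral t).

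**4. What can be detected for complications?** The sham mean m is an assumption, varied from 0.5 to 5 per patient. For an unadjusted log-rate comparison with variance φ × mean, 80% power requires

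|ln RR| = (2.409 + .842) × sqrt(φ × [1/(30m) + 1/(90·m·RR)]).

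Example with m = 1, φ = 1: at RR = .458 the left side is .781 and the right side is 3.251 × sqrt(.0333 + .0243) = .780. That is a 54% reduction.

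Power for a given reduction is Φ(|ln RR|/SE − 2.409), plus a negligible opposite tail. For a 30% reduction at m = 1: .357 / sqrt(1/30 + 1/63) = 1.608, so power = Φ(−.801) = .21.

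| Sham mean | Reduction for 80% power, φ=1 | Same, φ=2 | Power at 20% reduction, φ=1 / φ=2 | Power at 30% reduction, φ=1 / φ=2 |
|---|---|---|---|---|
| 0.5 | 71% | no solution with this formula | .05 / .03 | .10 / .05 |
| 1 | 54% | 71% | .08 / .05 | .21 / .10 |
| 2 | 41% | 54% | .17 / .08 | .45 / .21 |
| 3 | 34% | 46% | .26 / .12 | .65 / .33 |
| 5 | 27% | 37% | .46 / .22 | .88 / .55 |

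**5. Does the choice of test drive this?** The plan specifies a regression on the mean count. A simulated t-test on Poisson counts, which is nearer to that, gives power for a 30% reduction of .12, .22, .44 and .63 at sham means of 0.5, 1, 2 and 3. These are close to the log-rate figures.

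**6. Direct conversion of d=.70.** This is a separate calculation. With Poisson variance pooled over 30 and 90 patients, (m − m₁)/sqrt(.25m + .75m₁) = .70, where m₁ is the active-group mean. It gives reductions of 69%, 54%, 41%, 35% and 28% at sham means of 0.5, 1, 2, 3 and 5.

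**The case against.** The best defence has five parts.

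- **The number is correct.** This stands: there is no calculation error in the >.80 at d=.70. The defect is applying it to an outcome with no measured effect.
- **The event rate may be high.** The definition takes in nausea, vomiting and headache, and Table 1 records complications from PACU to 6 months, although Aim 1 speaks of the 48-hour period. Means above 2 are possible. At a mean of 5 with Poisson counts, power for a 30% reduction is .88. This stands too. A reader might infer that d=.70 simply means 41% to 71% fewer events, or that the trial has little chance of answering the question. The documents support neither: that range needs an assumed mean of 0.5 to 2 and Poisson counts, and its 71% end comes from the 80%-power calculation (step 4), not from converting d (step 6). Overdispersion, which is plausible for such a mixed count, pushes the detectable reduction back up, but the documents are silent on that as well.
- **The TKA pilot's safety sentence may concern the device only.** The sentence that follows it is about stopping tDCS for discomfort or device complications. It is thus weak evidence on complication rates. The point does not need it; the absence of any complication effect or rate is enough. Nor do the documents show that no pilot ever measured complications, only that none is reported.
- **Complications may not be primary.** Hypothesis 1 labels PCA use primary and pain secondary, and leaves complications unlabelled. But Section D lists them as primary and its alpha fits three outcomes.
- **The planned model is covariate-adjusted.** The figures above are unadjusted. Useful covariates could raise power somewhat, by an amount the documents do not let one estimate.

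**Conclusion.** The >.80 is unsupported for complications. It covers that outcome by its wording and its alpha, and nothing in the preliminary studies supplies an effect, rate or SD for it.

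How far the true power falls short cannot be fixed from the documents. Over assumed sham means of 0.5 to 5, with 90 and 30 patients analysed and a two-sided alpha of .016, the reduction needed for 80% power runs from 71% down to 27% under Poisson variance, and from 71% to 37% at means of 1 to 5 if variance is twice the mean. A 20% reduction would be missed more often than found in every case tried.

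A reader might also infer that a null complication result will be read as evidence of no effect. The wording of the power claim invites that, but no section states such a rule, and the trial is described as a pilot that informs whether a larger one is needed. The point is therefore one of unsupported justification, worth correcting because correction is cheap.

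**What to change.** 1. Remove complications from the >.80 statement in Section D.
2. For complications, state the detectable reduction over a range of assumed sham means (for example 0.5 to 5 per patient), with and without overdispersion, and say over which time window the count is taken.
3. Keep the planned test, and report the estimated rate ratio with its confidence interval beside it. Since the test stays, the three-way alpha split need not change.
4. Do not reaffirm >.80 for PCA dose as part of this edit. First reconcile d=.70, described as the most conservative pilot estimate, with the d=.38 for opioid use in the ERCP pilot.

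The cost is a less favourable stated figure and a little extra analysis work. No additional patients and no design change are needed.

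### The Aim-1 power statement calls d = .70 the most conservative pilot estimate, but the protocol prints d = .38 for one of its own tDCS pilots

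*Combined protocol and SAP*

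**What the plan says.** For Aim 1, Section D (Statistical Analysis and Power) states that "participants receiving any active tDCS (groups 1,2 & 3) will be collapsed and compared to the sham-only group", giving 90 active against 30 sham patients. Power is stated to exceed .80 at alpha .016, a level corrected for several outcomes, and the input is introduced with the words "Using the most conservative effect-size estimate from our series of pilot studies ($d=.70". The same value serves three primary outcomes: "total post-op PCA morphine-equivalent dose, VAS pain-on-average ratings, and mean number of post-operative complications". The analysis is covariate-adjusted: the listed variables "will be entered into the model as covariates to permit for statistical control of these potentially confounding variables".

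Section C (Preliminary Studies) reports two post-procedural tDCS pilots:

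- **Post-ERCP pilot** (19 patients, one 20-minute session). Patients on real tDCS "used 22% less total hydromorphone than those that received sham at the end of the 24-hour inpatient post-procedural period (Cohen's $d=.38". For pain, "VAS pain scores suggested an arithmetic advantage for real tDCS compared to sham (not statistically significant likely due to limited power"; no d is given.
- **TKA pilot** (40 patients, four sessions). Patients on real tDCS "used 44% less PCA dilaudid at 48-hours post-op ($p=.007$; Cohen's $d=1.0". For pain, "VAS ratings of pain-on-average were also significantly lower in the real tDCS group ($t(37)=2.28, p=.029"; again no d is given.

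No pilot d is printed for complications.

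**The concern.** A reader of Section D will conclude that power exceeds .80 even at the least favourable effect seen in the pilots. Section C contradicts that with a printed value of .38, for PCA opioid use, which Hypothesis 1 names as the primary outcome.

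The protocol says the findings will help decide whether a larger multi-site trial is needed (Section D, Impact on Clinical Practice and Future Studies). Someone who trusts the label could take a non-significant Aim-1 result as evidence against the whole range of pilot effects, when the design has little power at the lower end of that range.

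**Working it through.** **Inputs.** From Section D: 90 active, 30 sham, alpha .016, d = .70. From Section C: d = .38 and d = 1.0, both for opioid use, and t(37) = 2.28 for pain in the TKA pilot. Sidedness is not stated, so two-sided is assumed. d = .50 is an intermediate illustration. No variance explained by covariates (R²) is given, so R² values are assumptions.

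**Formula.** Two-sample comparison of means, noncentral t with df = 118:

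ncp = d × √(90 × 30 / 120) = d × √22.5 = 4.743 d

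The critical value is t(.992, 118) = 2.444.

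**The plan's own figure.** At d = .70, ncp = 3.32 and power = .808. The stated figure above .80 reproduces. With alpha = .05/3 power is .812, so the rounding of alpha does not matter.

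**Other effect sizes, unadjusted:**

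| d | ncp | power |
|---|---|---|
| .38 | 1.80 | .265 |
| .50 | 2.37 | .474 |
| .70 | 3.32 | .808 |
| 1.0 | 4.74 | .989 |

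The effect detectable with 80% power is d = .694, so there is almost no slack below .70.

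**Covariate-adjusted.** Divide ncp by √(1 − R²). With nine covariates, df = 120 − 2 − 9 = 109.

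| R² (assumed) | power at .38 | power at .50 | power at .70 | detectable d |
|---|---|---|---|---|
| .10 | .297 | .523 | .852 | .659 |
| .20 | .337 | .582 | .895 | .621 |
| .30 | .389 | .651 | .934 | .581 |

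Power at d = .38 is .54 at R² = .50 and reaches about .80 only near R² = .70.

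**Where .70 might come from.** No printed pilot result equals .70. If the TKA pain result is a simple two-group t, it implies 2.28 × √(1/20 + 1/19) = .73; the variants 2.28 × √(2/20) and 2 × 2.28/√37 give .72 and .75. The mean of the two printed values is (.38 + 1.0)/2 = .69. Either link is conjecture.

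**What a non-significant result could exclude.** The unadjusted 95% CI half-width is t(.975, 118)/4.743 = 1.980/4.743 = .417. Significance at .016 needs an observed d above 2.444/4.743 = .515. The upper limit falls below .38 only if the observed d is below .38 − .417 = −.037. So any observed d from about −.04 to .51 is non-significant and leaves .38 inside its interval. This concerns the pooled active arm, not a single session.

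**The case against.** The best defence is that .38 is the wrong yardstick. It comes from one session, a 24-hour window, a different electrode placement and an endoscopic procedure, whereas the Aim-1 arm pools four, two and one active sessions and Hypothesis 2a expects more sessions to do better. As an illustration, assume a straight line between the two printed opioid effects. Two sessions then give .38 + .62/3 = .59, the pooled mean is (.38 + .59 + 1.0)/3 = .66, and unadjusted power is about .75 (about .80 or .85 with R² of .10 or .20). The .38 is also imprecise: with 9 and 10 patients per group (assumed), its approximate 95% CI is .38 ± 1.96 × .464, or −.53 to 1.29, which contains both .70 and 1.0. Figure 9, on power by sample size, is not available here and may show other effect sizes. The protocol also calls the study a pilot, and the stated power is arithmetically right.

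Much of this stands, and it is why .26 should be read as a lower-end scenario rather than as the power to expect. It does not rescue the label. No figure can make .70 smaller than a printed .38, and the protocol gives no reason for leaving the ERCP pilot out. It relies on two independent tDCS pilots as the basis for the trial, and Group 3, one third of the pooled active arm, itself receives a single active session.

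**Conclusion.** The concern holds. The power calculation is correct for its input, but the description of that input contradicts Section C, so power above .80 is not a lower-end figure. Over the two printed opioid-use effects, unadjusted power runs from about .26 (d = .38) to .99 (d = 1.0). Adjustment with R² of .10 to .30 raises the lower end only to .30 to .39. These values assume a two-sided test and the full 120 patients analysed. The two printed effects concern opioid use only; the documents give no pilot d for pain ratings or complications, so they are not a range for all three primary outcomes. This should be fixed, because the sentence is wrong as written and affects how a null result will be read.

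**What to change.** In Section D, Statistical Analysis and Power:

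- Delete the description of .70 as the most conservative estimate, and state which pilot and which outcome it comes from. If the ERCP pilot is set aside, say so and give the reason.
- Print power of about .26, .47, .81 and .99 at d = .38, .50, .70 and 1.0, labelled unadjusted and two-sided at alpha .016. Describe .38 and 1.0 as the two printed opioid-use effects, and note that .38 rests on 19 patients.
- State that the effect detectable with 80% power is about d = .69 unadjusted, or about .62 if covariates explain 20% of the variance (an assumption).
- Add that a non-significant Aim-1 result may not exclude a smaller effect such as .38 and should be read from its confidence interval.

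The cost is one reworded paragraph, one line of power values and a less favourable stated figure. Enrolment, design and analysis do not change.
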